5.1 Analysis Populations

Safety population is defined as all subjects who are randomized and have received at least one dose of study products.

The intent to treat (ITT) population is defined as those subjects who are randomized, receive at least one dose of study product and have at least one post-baseline efficacy measurement.

The Per Protocol (PP) population will be a subset of the ITT population. Subjects with a protocol violation that is deemed to affect efficacy for all efficacy assessments will be excluded from the PP population. Subjects with a protocol violation that is deemed to affect efficacy for only some (but not all) of the efficacy assessments will be part of the PP population, but their data will be excluded from the assessment at which the protocol violation occurred. Efficacy analysis will be based on ITT population. A PP analysis will be performed only if 10% or more ITT subjects are excluded from PP population.

The repeatability population is defined as all subjects who have a repeat clinical assessment (TPI) at any visit.

Any of the following will be considered a protocol violation which will warrant exclusion from efficacy analysis:

- Violation of inclusion or exclusion criteria that are deemed to affect efficacy.
- Medical history which is deemed to affect efficacy.
- Use of prohibited treatment or medication before or during the study, which is felt to affect the assessment of efficacy.

 GlaxoSmithKline	Document Name	206886 SAP		
	Type	Version	Document Identifier	Effective Date
	eldo_clinical_doc	1.0; CURRENT; Most-Recent; Effective	090032d580cd9b2d	04-Jan-2017 09:07:54
	Reason For Issue	Auto Issue		

- Not receiving randomized treatment.
- Noncompliance on treatment washout

Further data listings will be included in the review of protocol violations but will be reviewed on a case-by-case basis to determine whether the data should be excluded from a PP. Full data listings will be provided in review listing requirement document.

Protocol violations which warrant exclusion from efficacy analysis will be identified between the statistician and medical director or designee, ahead of database lock and breaking the study blind.

5.2 Subgroups/Stratification

There is no subgroup/Stratification in this study.

5.3 Time Windows

The study schedule should be followed as per protocol. Deviations from the study schedule with respect to visit timings will be reviewed on a case-by-case basis to determine whether the data should be excluded from PP analysis. Required time windows are presented below:

- Visit 2 – 7-28 days from Visit 1
- Visit 3 – 4-6 days from Visit 2
- Visit 4 – 4-6 days from Visit 3
- Visit 5 – 4-6 days from Visit 4
- Visit 6 – 4-6 days from Visit 5.

6 Demographics and Baseline Characteristics

6.1 Subject Disposition

The subject disposition summary will include the number of screened subjects and screen failures overall and the number of subjects randomised per treatment group and overall.

The number and percentage of subjects, in the Safety, ITT and PP populations will be presented per treatment group and overall. The percentages will be based upon the total number of subjects randomised.

 GlaxoSmithKline	Document Name	206886 SAP		
	Type	Version	Document Identifier	Effective Date
	eldo_clinical_doc	1.0; CURRENT; Most-Recent; Effective	090032d580cd9b2d	04-Jan-2017 09:07:54
	Reason For Issue	Auto Issue		

The number and percentage of subjects completing the study and not completing the study, including a breakdown of the reasons for not completing the study, will be presented per treatment group and overall. The percentages are based upon the total number of subjects randomised.

A separate summary table of protocol violations leading to exclusion from PP analyses will be produced indicating the number and percentage of subjects with each violation per treatment group and overall. Percentages will be based on the ITT population.

6.2 Demographics

Descriptive statistics (number of subjects, mean, standard deviation, median, minimum and maximum for continuous variables, and frequency and percentage for categorical variables) will be provided for demographic data. These data include age, gender and ethnicity and will be presented for the Safety, ITT and PP populations.

6.3 Baseline Characteristics

Baseline efficacy measurements will be summarised in efficacy tables.

7 Treatment Compliance and Concomitant Medications

7.1 Treatment Compliance

Treatment compliance will be reviewed during blinded review and a listing will be produced for evaluation of protocol violations only. Non-compliance for extra/missed brushing will be assessed on a subject by subject basis. The data which are regarded as influenced by treatment non-compliance will be excluded from PP analysis. Any subject and/or time point excluded from PP analysis will be clearly documented in population definition document.

7.2 Concomitant Medications

Concomitant medication data will not be presented in the study report. A listing of concomitant medications will be produced for evaluation of protocol violators only.

8 Efficacy Analysis

Turesky modification of Quigley Hein Plaque Index (TPI) is the efficacy measure of the study. Treatment comparisons are under the hypotheses: H_0 : 'treatment difference

 GlaxoSmithKline	Document Name	206886 SAP		
	Type	Version	Document Identifier	Effective Date
	eldo_clinical_doc	1.0; CURRENT; Most-Recent; Effective	090032d580cd9b2d	04-Jan-2017 09:07:54
	Reason For Issue	Auto Issue		

is null' vs. H_a : 'treatment difference is not null'. All statistical tests will be conducted at the two-sided 5% significance level. All analysis will be conducted in SAS 9.2. The primary population for analysis will be ITT population.

8.1 Primary Efficacy Analysis

Primary efficacy endpoint will be the TPI score change from pre-brushing after a single brushing treatment. TPI score will be calculated as the average index over all tooth sites. Mixed effect ANCOVA model will be applied with treatment, study period as fixed effects, subject as a random effect and two baseline terms as covariates; (i) the subject-level baseline score calculated as the mean pre-brushing score across all periods within a subject, and (ii) the period level baseline minus the subject-level baseline. P-values for treatment comparisons, adjusted means of all treatments and treatment differences and their 95% CIs will be provided.

The primary analysis will be the comparison between the positive control and the negative control.

The assumption of residual normality and variance homogeneity in ANCOVA analysis will be investigated. If violated, data transformation or a non-parametric method (e.g., the Wilcoxon Signed-Rank test) will be applied. If violation is caused by several extreme values, a sensitivity analysis may be conducted by removing the extreme values.

8.2 Secondary Efficacy Analysis

Only if the primary objective is met (comparison of 67% w/w sodium bicarbonate, versus a 0% sodium bicarbonate is significant at two-sided 5% level), will the remaining secondary analyses be fully conducted. Otherwise no P-values will be provided for secondary comparisons. Only the estimates of treatment differences and confidence intervals will be provided.

Secondary analyses include the following treatment comparisons:

1. 50% sodium bicarbonate dentifrice versus a 0% sodium bicarbonate dentifrice;
2. 35% sodium bicarbonate dentifrice versus a 0% sodium bicarbonate dentifrice;
3. 20% sodium bicarbonate dentifrice versus a 0% sodium bicarbonate dentifrice;
4. 50% sodium bicarbonate dentifrice versus a 67% sodium bicarbonate dentifrice;
5. 35% sodium bicarbonate dentifrice versus a 67% sodium bicarbonate dentifrice;
6. 20% sodium bicarbonate dentifrice versus a 67% sodium bicarbonate dentifrice.

 GlaxoSmithKline	Document Name	206886 SAP		
	Type	Version	Document Identifier	Effective Date
	eldo_clinical_doc	1.0; CURRENT; Most-Recent; Effective	090032d580cd9b2d	04-Jan-2017 09:07:54
	Reason For Issue	Auto Issue		

The analyses will be carried out by the same ANCOVA model in primary analysis.

In the ANCOVA analysis of the effects of the five treatments with different levels of sodium bicarbonate (0%, 20%, 35%, 50%, 67%), the linear and quadratic contracts will be tested for dose-response trend if the difference between the highest dose (67%) and lowest dose (0%) is significant. When a trend is significant (significance level 5%), a mixed effect regression (linear, quadratic etc) will be run to provide dose-response regression curve. For example the quadratic regression will take dose and dose² as explanatory variables and subject as random effect. The regression curve will be plotted together with the dose-response data. If neither linear model nor quadratic model appears to fit the data well (through residual check), other nonlinear models may also be considered.

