Repeatability of plaque assessment in selection of subjects	X	X	X	X	X	X
Inclusion/Exclusion criteria	X ¹	X ¹				
Dispense wash-out toothpaste, toothbrush, countdown timer and diary card with verbal instructions	X					
Return wash-out toothpaste, toothbrush and diary card		X	X	X	X	X
Re-dispense wash-out toothpaste, toothbrush and diary card		X	X	X	X	
Pre-brushing plaque disclosure		X	X	X	X	X
Pre-brushing plaque assessment		X	X	X	X	X
Randomisation		X				
Supervised brushing with assigned toothpaste		X	X	X	X	X
Post brushing plaque disclosure		X	X	X	X	X
Post-brushing plaque assessment ²		X	X	X	X	X
Brushing with washout toothpaste to remove stain from disclosing dye	X	X	X	X	X	X
Compliance check		X	X	X	X	X
Subject Adherence/Eligibility check		X	X	X	X	X
Adverse events	X	X	X	X	X	X
Study Conclusion						X

¹ Plaque (inclusion criteria 4 C) will be assessed at Visit 1 and Visit 2; use of antibiotics and Chlorhexidine mouthwashes (exclusion criteria 7 A and 8 K) at Visit 2 to determine eligibility to continue.

 GlaxoSmithKline	Document Name	206886 Protocol		
	Type	Version	Document Identifier	Effective Date
	eldo_clinical_doc	1.0; CURRENT; Most-Recent; Effective	090032d580c3d7b4	27-Oct-2016 12:48:36
	Reason For Issue	Auto Issue		

PROTOCOL SYNOPSIS FOR STUDY 206886

Brief Summary

This will be a single centre, , controlled, examiner blind, five treatment, five period, crossover design study in healthy volunteers. This study will evaluate the dose response of three experimental toothpastes containing 20%, 35% and 50% w/w sodium bicarbonate to remove plaque after a single brushing, compared to a positive control (67% w/w sodium bicarbonate) and negative control (0% w/w sodium bicarbonate) dentifrice.

This clinical study will be conducted at proDERM Institute, Germany and funded by GlaxoSmithKline Consumer Healthcare (GSK CH).

Objectives and Endpoints

Primary	Endpoint

 To evaluate and compare the plaque removal efficacy, as measured by Turesky modification of Quigley Hein Plaque Index (TPI), of 67% w/w sodium bicarbonate, versus a 0% sodium bicarbonate toothpaste. 	
 Change from Pre-brushing to Post-brushing TPI
Secondary	Endpoint

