9.3.3. Secondary Analysis

Secondary analyses include the following treatment comparisons:

1. 50% sodium bicarbonate dentifrice versus a 0% sodium bicarbonate dentifrice;
2. 35% sodium bicarbonate dentifrice versus a 0% sodium bicarbonate dentifrice;
3. 20% sodium bicarbonate dentifrice versus a 0% sodium bicarbonate dentifrice;
4. 50% sodium bicarbonate dentifrice versus a 67% sodium bicarbonate dentifrice;
5. 35% sodium bicarbonate dentifrice versus a 67% sodium bicarbonate dentifrice;
6. 20% sodium bicarbonate dentifrice versus a 67% sodium bicarbonate dentifrice.

The analyses will be carried out by the same ANCOVA model in primary analysis. P-values for treatment comparisons, adjusted means of all treatments and treatment differences and their 95% CIs will be provided.

In the ANCOVA analysis of the effects of the five treatments with different contents of sodium bicarbonate (0%, 20%, 35%, 50%, 67%), the linear and quadratic contracts will be tested for dose-response trend. When a trend is significant, a mixed effect regression (linear, quadratic etc) will be run to provide dose-response curve. The regression curve will be plotted together with the dose-response data. If neither linear

 GlaxoSmithKline	Document Name	206886 Protocol		
	Type	Version	Document Identifier	Effective Date
	eldo_clinical_doc	1.0; CURRENT; Most-Recent; Effective	090032d580c3d7b4	27-Oct-2016 12:48:36
	Reason For Issue	Auto Issue		

model nor quadratic model appears to fit the data well, other nonlinear models may also be considered.

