Appendix 2 List of Tables, Figures & Listings

Table No.	Table Title (including population)	Standard	Template
9.1.1.1	Subject Disposition By Treatment Group – All Screened Subjects	X	
9.1.1.2	Subject Disposition By Treatment Group and Study Period – All Screened Subjects	X	
9.1.2	Protocol Violations Leading To Exclusion From Per Protocol Analysis – ITT Population	X	
9.2.1.1	Demographic Characteristics – Safety Population	X	
9.2.1.2	Demographic Characteristics – ITT Population	X	
9.3.1.1	Analysis Of Turesky Plaque Score Change from Pre-brushing – ITT Population		App 3
9.3.1.2*	Analysis Of Turesky Plaque Score Change from Pre-brushing – PP Population		9.3.1.1
9.3.2	Repeatability Analysis Of Turesky Plaque Index – Repeatability Population		App 3
9.4.1.1**	Listing Of Adverse Events – Safety Population	X	
9.4.1.2**	Listing Of Serious Adverse Events – Safety Population	X	
9.4.2	Treatment Emergent Adverse Events By Oral/Non Oral And PT – Safety Population	X	
9.4.3	Treatment Emergent Treatment Related Adverse Events By Oral/Non Oral And PT – Safety Population	X	
9.4.4	Treatment Emergent Adverse Events By SOC And PT – Safety Population	X	
9.4.5***	Treatment Emergent Non-Serious Adverse Events By SOC And PT – Safety Population	X	

*provided only if PP analysis is done.

** If there are non AEs a NULL listing will be provided. For 9.4.1.2, if there are more than 5 serious AEs a table will be done instead of listing.

	Document Name	206886 SAP		
	Type	Version	Document Identifier	Effective Date
	eldo_clinical_doc	1.0; CURRENT; Most-Recent; Effective	090032d580cd9b2d	04-Jan-2017 09:07:54
	Reason For Issue	Auto Issue		

*** Provided only if there are more than 5 serious AEs.

FIGURES

Figure No.	Figure Title (including population)	Standard	Template
9.1	Mean Turesky Plaque Score By Treatment – ITT Population		App 3
9.2	Scatter Plot With Regression Curve Over Dose Range [0,67] (% sodium bicarbonate) – ITT Population		App 3

 GlaxoSmithKline	Document Name	206886 SAP		
	Type	Version	Document Identifier	Effective Date
	eldc_clinical_doc	1.0: CURRENT: Most-Recent: Effective	090032d580cd9b2d	04 Jan 2017 09:07:54
	Reason For Issue	Auto Issue		

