Appendix 3 Templates for Tables, Figures & Listing

Treatment headers will be: Test 1; Test 2; Test 3; Positive Control; Negative Control.

For all tables add footnotes

Test 1: Experimental dentifrice containing 20% w/w sodium bicarbonate

Test 2: Experimental dentifrice containing 35% w/w sodium bicarbonate

Test 3: Experimental dentifrice containing 50% w/w sodium bicarbonate

Positive Control: Dentifrice containing 67% w/w sodium bicarbonate (German marketed Parodontax Classic (non-fluoride) Toothpaste)

Negative Control: Dentifrice containing 0% w/w sodium bicarbonate (UK marketed Macleans Fresh Mint Toothpaste - 1450 ppm Fluoride)

CCI

 GlaxoSmithKline	Document Name	206886 SAP		
	Type	Version	Document Identifier	Effective Date
	eldo_clinical_doc	1.0: CURRENT: Most Recent: Effective	090032d580cd9b2d	04 Jan 2017 09:07:54
	Reason For Issue	Auto Issue		

Protocol: 206886

Program Run Date: ddmonyyyy

Table 9.3.1.1
 Analysis Of Turesky Plaque Score Change from Pre-brushing
 ITT Population

Study Population: ITT (N=xxx)

	Test 1 (N=xx)		Test 2 (N=xx)		...	Positive Control (N=xxx)		Negative Control (N=xx)	
	Raw	Change	Raw	Change		Raw	Change	Raw	Change
Pre-brushing									
N*	XX		XX		...	XX		XX	
MEAN	X.XX		X.XX		...	X.XX		X.XX	
SD	X.XXX		X.XXX		...	X.XXX		X.XXX	
SE	X.XXX		X.XXX		...	X.XXX		X.XXX	
MEDIAN	X.XX		X.XX		...	X.XX		X.XX	
MINIMUM	X.X		X.X		...	X.X		X.X	
MAXIMUM	X.X		X.X		...	X.X		X.X	
Post-brushing									
N*	XX	XX	XX	XX	...	XX	XX	XX	XX
MEAN	X.XX	X.XX	X.XX	X.XX	...	X.XX	X.XX	X.XX	X.XX
SD	X.XXX	X.XXX	X.XXX	X.XXX	...	X.XXX	X.XXX	X.XXX	X.XXX
SE	X.XXX	X.XXX	X.XXX	X.XXX	...	X.XXX	X.XXX	X.XXX	X.XXX
MEDIAN	X.XX	X.XX	X.XX	X.XX	...	X.XX	X.XX	X.XX	X.XX
MINIMUM	X.X	X.X	X.X	X.X	...	X.X	X.X	X.X	X.X
MAXIMUM	X.X	X.X	X.X	X.X	...	X.X	X.X	X.X	X.X
ADJUSTED MEAN [1]		X.XX	X.XX	X.XX	...	X.XX	X.XX	X.XX	X.XX
SE [1]		X.XXX	X.XXX	X.XXX	...	X.XXX	X.XXX	X.XXX	X.XXX
TREATMENT COMPARISONS [1]	DIFFERENCE(CI)[1][2]				P-VALUE[1]				
Pos.Control vs. Neg.Control	X.XX (X.XX, X.XX)				0.XXXX				
Test 1 vs. Neg.Control	X.XX (X.XX, X.XX)				0.XXXX**				
Test 2 vs. Neg.Control	X.XX (X.XX, X.XX)				0.XXXX**				
Test.3 vs. Neg.Control	X.XX (X.XX, X.XX)				0.XXXX**				
Test 1 vs. Pos.Control	X.XX (X.XX, X.XX)				0.XXXX**				
Test.2 vs. Pos.Control	X.XX (X.XX, X.XX)				0.XXXX**				
Test 3 vs. Pos.Control	X.XX (X.XX, X.XX)				0.XXXX**				
Linear Contrast					0.XXXX**				
Quadratic Contrast					0.XXXX**				

*Number of subjects with non-missing values

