**P-value for test products against two controls will be provided only if Pos.Control vs neg.Control is significant.

[1] From ANCOVA analysis for change from pre-brushing with treatment and period as fixed effect, subject as random effect, subject-level baseline and period-level minus subject-level baseline as covariates.

[2] Difference is first named treatment minus second named treatment such that a negative difference favors the first named treatment

(Page X of Y)

PPD

PPD

 GlaxoSmithKline	Document Name	206886 SAP		
	Type	Version	Document Identifier	Effective Date
	eldc_clinical_doc	1.0: CURRENT: Most-Recent: Effective	090032d580cd9b2d	04 Jan 2017 09:07:54
	Reason For Issue	Auto Issue		

	Document Name	206886 SAP	
	Type	Version	Document Identifier
	eldo_clinical_doc	1.0: CURRENT: Most-Recent: Effective	090032d580cd9b2d
	Reason For Issue	Auto Issue	
			Effective Date
			04 Jan 2017 09:07:54

Protocol: 206886

Program Run Date: ddmonyyyy

Table 9.3.2
 Repeatability Analysis of Turesky Plaque Index
 Repeatability Population

Study Population: Repeatability (N=xx)

First Assessment [1]	Second Assessment					
	Missing	0	1	2	3	4
MISSING	XX	XX	XX	XX	XX	XX
0	XX	XX (xx.x%)				
1	XX	XX (xx.x%)				
2	XX	XX (xx.x%)				
3	XX	XX (xx.x%)				
4	XX	XX (xx.x%)				

WEIGHTED KAPPA = 0.xxx

95% C.I. = 0.xxx, 0.xxx

Note: Percentages are based on total of all non-missing combinations

[1] The first assessment is the one used in the efficacy analysis.

0: No plaque

1: Slight flecks of plaque at the cervical margin of the tooth

2: A thin continuous band of plaque (1 mm or smaller) at the cervical margin of the tooth

3: A band of plaque wider than 1 mm but covering less than 1/3 of the crown of the tooth

4: Plaque covering at least 1/3 but less than 2/3 of the crown of the tooth

5: Plaque covering 2/3 or more of the crown of the tooth

(Page X of Y)

PPD

PPD

[figure not shown]
	Document Name	206886 SAP		
	Type	Version	Document Identifier	Effective Date
	eldo_clinical_doc	1.0: CURRENT, Most-Recent, Effective	090032d4580cd9b2d	04 Jan 2017 09:07:54
	Reason For Issue	Auto Issue		

Protocol: 206886

Program Run Date: DDMMYYYY

Figure 9.1
 Mean TPI change from pre-brushing (\pm SE) by treatment
 ITT Population

Study Population: ITT (N=xxx)

PPD

PPD

[figure not shown]
	Document Name	206886 SAP	
	Type	Version	Document Identifier
	eldo_clinical_doc	1.0: CURRENT: Most-Recent: Effective	090032d580cd9b2d
	Reason For Issue	Auto Issue	
			Effective Date

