			04 Jan 2017 09:07:54

Protocol: 206886

Program Run Date: DDMMYYYY

Figure 9.2
Scatter plot with regression curve over dose range [0,67] (% sodium bicarbonate)
ITT Population

Study Population: ITT (N=xxx)

Regression curve: $TPI\ change = a + b \cdot dose + c \cdot dose^2$ from mixed effect model with dose, $dose^2$ as regressors and subject as random effect.

PPD

PPD

Document Name	206886 SAP		
Type	Version	Document Identifier	Effective Date
eldo_clinical_doc	1.0; CURRENT; Most-Recent; Effective	090032d580cd9b2d	04-Jan-2017 09:07:54
Reason For Issue	Auto Issue		

SIGNATURE PAGE

206886 SAP

Date	Signed By
03-Jan-2017 10:59:49	PPD
Justification	Biostatistics Approval

Date	Signed By
04-Jan-2017 09:07:47	PPD
Justification	Approved

Date	Signed By
Justification	

Date	Signed By
Justification	

Date	Signed By
Justification	

Date	Signed By
Justification

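### The dose-response curve leaves out the period and baseline terms of the model that tests the trend, so it may be less precise than the data allow (minor)

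*SAP*

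**What the plan says.** Two models address the same dose-response question.

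- **Trend test.** SAP 8.1 specifies: "Mixed effect ANCOVA model will be applied with treatment, study period as fixed effects, subject as a random effect and two baseline terms as covariates". The baseline terms are the subject's mean pre-brushing score over all periods and each period's deviation from that mean. SAP 8.2 tests the linear and quadratic contrasts in this model. Footnote [1] to Table 9.3.1.1 (Appendix 3) confirms the adjustment for "subject-level baseline and period-level minus subject-level baseline as covariates".
- **Curve.** If a trend is significant, SAP 8.2 fits a separate regression: "For example the quadratic regression will take dose and dose² as explanatory variables and subject as random effect". The Figure 9.2 footnote gives a quadratic equation for TPI change, with dose and dose squared "as regressors and subject as random effect". Neither place mentions period or baseline.

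Protocol 9.3.3 says only that "a mixed effect regression (linear, quadratic etc) will be run to provide dose-response curve" and lists no covariates. The Protocol Synopsis (Brief Summary) gives the purpose: "This study will evaluate the dose response of three experimental toothpastes".

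**The concern.** The sponsor judged period and both baseline terms worth including when testing the trend, but drops them without comment when drawing it. If pre-brushing deviation helps predict the change in TPI, leaving it out puts explainable variation into the residual and makes the dose coefficients noisier.

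Table 9.3.1.1 already reports adjusted means at the five tested doses, and pairwise differences with intervals. Figure 9.2 is the only planned description of the response between those doses, over 0% to 67%. A reader could see a curve that departs from the adjusted means because the covariates differ, not because of dose. The text mentions no standard error or band for the curve that would show how much of this is noise. The residual check that decides between linear, quadratic and other shapes would also be made on the unadjusted fit.

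**Working it through.** **Inputs from the documents (SAP 4).** SD of the between-treatment difference 0.32; 50 completers; design difference 0.15 TPI; 90% power. Doses are 0, 20, 35, 50 and 67%.

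**Plan's own figure.** Paired t-test, noncentrality 0.15/0.32 × √50 = 3.315, 49 df, two-sided 0.05: power 0.901. The stated 90% reproduces, and this point does not touch it.

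**Assumptions, not in the documents.** r is the within-subject correlation between baseline deviation and change, taken as 0, 0.3, 0.5 or 0.6. Data are complete, there is no period effect, and 0.32 is an SD without baseline adjustment.

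**Which omitted terms matter.** With complete data the subject-level baseline is constant within a subject, so it shifts the height of the curve and not its slope. With balanced sequences the period term leaves the fitted dose effect essentially unchanged. Any gain then comes from the period-level deviation, which multiplies the residual SD by √(1 − r²).

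**Linear fit, change from 0% to 67%.**
- Per-visit SD = 0.32/√2 = 0.2263.
- Mean dose 34.4; sum of squared deviations 2697.2.
- SE without the terms = 67 × 0.2263/√(50 × 2697.2) = 0.0413.
- SE with them = 0.0413 × √(1 − r²).

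**Quadratic fit, change from 0% to dose x.** Variance = 0.2263² × q′(50 X′X)⁻¹q, where X holds the centred dose and dose squared at the five doses and q = (x, x²).

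| Fitted change from 0% | Without terms (same as r = 0) | r = 0.3 | r = 0.5 | r = 0.6 |
|---|---|---|---|---|
| to 67%, linear | 0.0413 | 0.0394 | 0.0358 | 0.0330 |
| to 27.5%, quadratic | 0.0363 | 0.0346 | 0.0314 | 0.0290 |
| to 42.5%, quadratic | 0.0403 | 0.0385 | 0.0349 | 0.0323 |
| to 58.5%, quadratic | 0.0388 | 0.0371 | 0.0336 | 0.0311 |
| SE ratio, without/with = 1/√(1 − r²) | 1.00 | 1.05 | 1.15 | 1.25 |

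**Simulation check.** 3000 runs per r, 50 subjects, 10-sequence Williams-type layout, no period effect. Ratios of sampling SDs, without to with the terms, at r = 0 / 0.3 / 0.5 / 0.6:
- linear, 0% to 67%: 0.995 / 1.044 / 1.145 / 1.266
- quadratic, 0% to 42.5%: 0.997 / 1.041 / 1.132 / 1.247

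**Disagreement between the two curves.** In the same runs the unadjusted and adjusted 0%-to-67% changes differed with SD 0.003 / 0.013 / 0.021 / 0.025 TPI. Against the 0.15 design difference the ends of this range are 0.003/0.15 = 2% and 0.025/0.15 = 17%.

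**If sequences are not balanced.** Protocol 3.4 says order is randomly allocated, and the documents do not describe the sequence layout. A second simulation (600 runs per setting, r from 0 to 0.5, quadratic fit) used unrestricted random orders and an assumed period-effect SD of 0 or 0.1 TPI. The ratio of sampling SDs for the 0%-to-67% change ran from about 0.99 to 1.28, and both fits were unbiased throughout.

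**The case against.** The strongest reply is that this is a modelling preference about a descriptive figure. The curve is drawn only after the primary comparison and then a trend are significant. The listed objectives are all pairwise comparisons, no decision rule uses the curve, and the study calls itself exploratory. The SAP offers the model as an example and allows other forms. An unadjusted curve also suits a scatter plot of raw data, and Table 9.3.1.1 sets raw and adjusted means side by side. The loss may be zero, and the 25% figure needs r = 0.6, which nothing in the documents supports or excludes.

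Most of this stands, and it is why the point is minor. Two parts do not carry. The wording as an example does not settle the matter, because the Figure 9.2 footnote repeats the reduced model without that qualifier; following the SAP as written gives the unadjusted curve. The match to the raw scatter is a fair consideration, but it can be handled by overlaying the adjusted means. The template drawing is not shown in the available text, so what it overlays or shades cannot be judged.

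**Conclusion.** The concern holds, as a minor point. It is clear that the terms are omitted; how much that costs is uncertain. With complete data and balanced sequences, the SE of the fitted curve is inflated by nothing at r = 0 and by about 25% at r = 0.6. With unrestricted random orders and a period effect, the inflation reached about 28% at r = 0.5. These sizes rest on an assumed r, an assumed period effect, and 0.32 being an SD without baseline adjustment. The contrast p-values, pairwise differences, intervals and adjusted means all come from the full ANCOVA and are untouched.

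**What to change.** In SAP 8.2 and the Figure 9.2 footnote, specify the curve as the primary mixed ANCOVA with dose (and dose squared) in place of the treatment factor, keeping study period, both baseline terms and random subject. Plot it at mean baseline averaged over periods, with the adjusted treatment means overlaid on the observed data.

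The cost is one line of SAP text, the footnote and the model code. Protocol 9.3.3 lists no covariates for this regression and need not change. Every term is already collected and already in the primary model. The fit spends about 6 degrees of freedom (4 for period, 2 for baseline) out of roughly 50 × 5 = 250 observations. The curve will no longer track the raw means exactly, which is the reason for the overlay. A polynomial still need not pass through the five adjusted means; the change removes only the disagreement caused by different covariates.
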